Drugs which affect platelet function (e.g., aspirin, NSAIDs, dipyridamole, ticlopidine, clopidogrel) may potentiate the risk of hemorrhage.

Thrombolytic agents increase the risk hemorrhage.

Warfarin: Risk of bleeding may be increased during concurrent therapy. Dalteparin is commonly continued during the initiation of warfarin therapy to assure anticoagulation and to protect against possible transient hypercoagulability.

Ethanol/Nutrition/Herb Interactions

Herb/Nutraceutical: Avoid cat's claw, dong quai, evening primrose, garlic, ginseng (all have additional antiplatelet activity).

Pharmacodynamics/Kinetics

Onset of action: 1 – 2 hours

Duration: >12 hours

Half-life elimination (route dependent): 2 – 5 hours

Time to peak, serum: 4 hours

Dosage

Adults: SubQ: 2500 units 1 – 2 hours prior to surgery, then once daily for 5 – 10 days postoperatively.

Monitoring Parameters

Periodic CBC including platelet count; stool occult blood tests (if clinically indicated with signs of gastrointestinal bleeding such as melena, vomiting of coffee grounds, abdominal pain, sudden drop of hemoglobin); monitoring of PT and PTT is not necessary.

Administration

Administration once daily beginning prior to surgery and continuing 5 – 10 days after surgery prevents deep vein thrombosis in patients at risk for thromboembolic complications.

Additional Information

Molecular weight: 5000; sulfur content: 11%

Dosage Forms

Injection:

Prefilled syringe: Anti-Factor Xa 2500 units per 0.2 mL; Anti-Factor Xa 5000 units per 0.2 mL

Multidose vial: 95,000 units anti-Factor Xa/Vial (9.5 mL vial) = 10,000 units/mL

Materials and Methods:

Patients

There will be two study groups:

Group A. Metastatic disease in the lower extremity requiring limited excision (curettage) of tumor as part of surgical treatment. Inclusion criteria would include all of the following:

1. Metastatic disease, myeloma, or lymphoma.
2. Pathologic fracture or impending pathologic fracture of the femur.
3. Intramedullary rod, plating, cementation, hip arthroplasty or knee arthroplasty.

Group B. Primary sarcoma of the lower extremity requiring radical resection of tumor. Inclusion criteria would include all of the following:

1. Primary sarcoma of bone or soft tissue of lower extremity.
2. T2 tumor (> 5 cm but < 20 cm).
3. Radical resection of tumor, which may necessitate major bone or soft tissue reconstruction.

Exclusion criteria for both groups would include the following:

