1. Presence of DVT on pre-operative screening ultrasound study.
2. Massive tumor (>20 cm in greatest dimension)
3. Amputation of the affected leg as treatment for tumor.
4. Estimated blood loss >2 liters during surgery.
5. Surgical drain output >500 cc of bloody fluid during first 8 hours.
6. I.N.R. >1.3 pre-operatively or > 1.5 post-operatively.
7. Platelet count < 100,000 either pre-operatively or post-operatively.
8. Indwelling post-operative epidural catheter for pain control.
9. Age <30 years.
10. History of underlying bleeding disorder, such as hemophilia.
11. History of adverse reaction to heparin such as heparin-induced thrombocytopenia.
12. Severe liver or renal insufficiency.
13. History of hypertensive or diabetic retinopathy.
14. History of gastro-intestinal bleeding within 12 months.
15. Treatment with warfarin, clopidogrel, aspirin, NSAIDs, LMWH or other anti-coagulants for conditions.
16. History of stroke.
17. Women of childbearing potential having a positive serum or urine pregnancy test (hCG) at the time of pre-operative evaluation (within 7 days of surgery).
18. Women who are breast feeding.
19. Hemoglobin < 8.0 gm/dl
20. Platelet count < 100,000 /L
21. Alanine aminotransferase >100 IU/L
22. Aspartate aminotransferase > 100 IU/L

23. Direct bilirubin >0.5 gm/dL (the laboratory does not perform direct bilirubin if total bilirubin is below 0.2 mg/dl since direct bilirubin cannot be greater than total bilirubin).
24. Serum creatinine > 2.0 gm/dL
25. Patients taking COX-2 inhibitors.
26. Patients who have fragmented mechanical heart valves.

Study Design

The study design will be an open-label, non-randomized clinical trial involving 25 – 35 consecutive patients in each of the two groups. Historical controls from this institution will be used to compare peri-operative bleeding events, drainage, transfusion requirements, and re-operation rates in similar patients who did not receive chemical prophylaxis for DVT. Published historical controls will be used to compare the DVT rate. The rate of DVT will be measured in this study, but the primary objective is to examine bleeding complications at the surgical site. The sample size therefore is not calculated to establish efficacy, which has been demonstrated for patients in general in numerous previous articles.

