The study design will be an open-label, non-randomized clinical trial involving 25 – 35 consecutive patients in each of the two groups. To analyze wound complications historical controls will be identified through the Surgical Database maintained by the Section of Orthopaedics from this institution and will be used to compare peri-operative bleeding events, drainage, transfusion requirements, and re-operation rates in similar patients who did not receive chemical prophylaxis for DVT. Data from surgery, including drain output, transfusion requirements, wound complications, and re-operation for wound problems will be collected. To analyze DVT rates and to compare against patients who did not receive, data from the previously published article by Lin et. al. will be used for the control group of patients with mechanical compression stockings alone. Patients will receive a combination of dalteparin, bilateral TED hose, and bilateral mechanical compression stockings while in the hospital.

Method of DVT Prophylaxis

Patients will receive a combination of dalteparin, bilateral TED hose, and bilateral mechanical compression stockings while in the hospital.

The reason for employing both mechanical prophylaxis and dalteparin together is as follows. DVT prophylaxis is very difficult to achieve. The DVT rate is never zero. There is a very little, if any, adverse effects of using mechanical compression stockings. However, from the previous study at Memorial Sloan-Kettering, it is known that there is still a significant rate of DVT (17%) with mechanical prophylaxis. Dalteparin and other low molecular weight heparins may improve upon this rate. There is no contraindication to using both dalteparin and mechanical prophylaxis together. The study is not intended to show that dalteparin obviates the need for mechanical prophylaxis.

Patients should not receive other anti-coagulants, such as aspirin, non-steroidal anti-inflammatory drugs, and warfarin while on the study. Heparin should not be administered except for routine intravenous catheter flushes.

During surgery, patients will have TED hose and a mechanical compression stocking on the unaffected extremity. For the operative leg TED hose and mechanical compression stocking will be applied in the recovery room.

Patients will be mobilized out of bed with physical therapy as soon as deemed safe by the attending physician (generally post-operative day 1).

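### Exclusions 4 to 7 screen trial patients on early bleeding and clotting values, but the plan does not say that the historical database controls must pass the same screen

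*Combined protocol and SAP*

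**What the plan says.** Under Materials and Methods, Patients, the protocol opens with "There will be two study groups" (A, metastatic; B, sarcoma), and the list that follows is headed "Exclusion criteria for both groups would include the following". Four entries use findings made during or after the operation, two of them alongside a pre-operative limit:

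- Early drainage, which is exclusion 5: "Surgical drain output >500 cc of bloody fluid during first 8 hours"
- Bleeding in the operating room, which is exclusion 4: "Estimated blood loss >2 liters during surgery"
- Low platelets, which is exclusion 7: "Platelet count < 100,000 either pre-operatively or post-operatively"
- Prolonged clotting, which is exclusion 6: "I.N.R. >1.3 pre-operatively or > 1.5 post-operatively"

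Under Study Design, "historical controls will be identified through the Surgical Database maintained by the Section of Orthopaedics from this institution". The section gives their purpose and the only rule for choosing them in these words: "used to compare peri-operative bleeding events, drainage, transfusion requirements, and re-operation rates in similar patients who did not receive chemical prophylaxis for DVT". Neither that section nor any other defines *similar* or applies exclusions 4 to 7 to the controls.

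Endpoints of Analysis, item 2, is cumulative drain output with no start time. The Analysis Plan gives means, medians, frequency tables and 95% confidence intervals; it contains no matching, adjustment or between-group method. Dosing of Dalteparin puts the first dose 12 to 24 hours after surgery.

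**The concern.** Purpose states the goal as finding out whether surgical-site bleeding complications are significantly increased. For drainage, transfusion and peri-operative bleeding events, the database controls are the only comparator named.

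An analyst could reasonably select controls by diagnosis, operation and absence of chemical prophylaxis. The trial group would then have been cleared of patients who bled heavily or had poor clotting values early on, and the control group would not. The first 8 hours of drainage would be both a condition of staying in the trial group and, as the endpoint is worded, part of the outcome. That difference cannot be a drug effect, because the drain window closes before the first dose. It would tend to make dalteparin look safer than it is, which is the wrong direction of error for a safety study meant to inform a larger trial.

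**Working it through.** The plan states no figure for this comparison, so there is none to reproduce.

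**1. First-8-hour drainage: direction is certain.** Let *f* be the share of patients removed by exclusion 5. Then unfiltered mean − kept mean = *f* × (mean of removed − mean of kept) ≥ *f* × (500 − mean of kept), treating all early drainage as bloody. With an assumed kept mean of 200 cc:

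| *f* (assumed) | smallest gap | as share of unfiltered mean |
|---|---|---|
| 5% | 0.05 × 300 = 15 cc | 15/215 = 7.0% |
| 10% | 30 cc | 30/230 = 13.0% |
| 20% | 60 cc | 60/260 = 23.1% |

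**2. Cumulative drainage: direction depends on correlation.** Assume that early (0–8 h) and later drainage are lognormal with medians *m* and *M*, log-SDs *s* and 0.7, and log-scale correlation ρ. With a = ln(500/*m*)/*s*:

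- share removed = 1 − Φ(a)
- kept early mean = *m*·exp(*s*²/2)·Φ(a − *s*)/Φ(a)
- kept later mean = *M*·exp(0.7²/2)·Φ(a − 0.7ρ)/Φ(a)

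The sarcoma grid, all inputs assumed, is *m* = 150, 200 or 300 cc; *s* = 0.6 or 0.8; *M* = 800 cc; ρ = 0, 0.3 or 0.7 (18 scenarios). Its two ends are:

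- *m* = 150, *s* = 0.6, ρ = 0: a = 2.007, 2.2% removed. Kept mean 169.0 + 1022.1 = 1191.1; unfiltered 179.6 + 1022.1 = 1201.7; ratio 0.991.
- *m* = 300, *s* = 0.8, ρ = 0.7: a = 0.639, 26% removed. Kept mean 243.9 + 773.8 = 1017.7; unfiltered 413.1 + 1022.1 = 1435.2; ratio 0.709.

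So the sarcoma mean falls by 1% to 29%, and the median, by simulation, by 1% to 20%. With metastatic inputs (*m* = 50, 100 or 150 cc, *M* = 200 cc), 0% to 7% of patients are removed and the mean falls by 0% to 14%. The smaller effect fits the Introduction, which expects little drainage in that group.

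At ρ = −0.3 the sarcoma mean is still 0% to 6% low. At ρ = −0.7 it is 0.5% to 3% high. The sign changes between −0.34 and −0.64, depending on the setting.

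**3. Sensitivity to the assumptions.** Changing only the later sarcoma median to 400, 1500 or 3000 cc moves the middle scenario's fall to about 10%, 6% or 4%. A separate set of assumptions (early median 300 cc, log-SD 1.0 for both periods, half of typical drainage early, ρ = 0.5) gives a fall of 41%. Counts of scenarios are therefore not probabilities, and no typical size can be claimed.

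**4. Masking.** Suppose that dalteparin truly raises sarcoma drainage after 8 hours by 20%.

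- Low end: (169.0 + 1.2 × 1022.1)/1201.7 = 1.161 with only the trial filtered; 1395.5/1191.1 = 1.172 with both filtered.
- High end: (243.9 + 1.2 × 773.8)/1435.2 = 0.817 with only the trial filtered; 1172.5/1017.7 = 1.152 with both filtered.

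Across the grid, filtering both groups gives 1.15 to 1.17. Filtering only the trial gives 0.82 to 1.16, below 1 in 4 of 18 scenarios. All four need 12% to 26% of patients removed, and three need ρ = 0.7. With later medians of 400 or 3000 cc the count is 7 or 2.

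**5. Against sampling error.** The 95% half-width of the difference, as a share of the control mean, is 1.98 × √[(CV_trial × ratio)²/n_trial + CV_control²/n_control], with CVs from the simulation. For 30 sarcoma patients against 30, 60 or 100 controls (number not given in the plan) it is 30–36%, 24–31% or 21–28%. The fall exceeds it in 0, 1 or 2 of 18 scenarios. For 25 metastatic patients against 25 to 100 controls it is 23% to 42% and is never exceeded.

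**6. Transfusion and bleeding events.** If the removed patients have *RR* times the risk of the rest, filtered/unfiltered rate = 1/(1 − *f* + *f* × *RR*). With *f* = 20% and *RR* = 3 this is 1/1.4 = 0.714. With *RR* = 1 it is 1. For *f* of 5% to 20% and *RR* of 1 to 3 (assumed), the trial rate is 0% to 29% lower in relative terms.

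**The case against.** The strongest reply is that *similar* may already mean patients who meet the same criteria. The blood-loss and 8-hour drain filters act before the first dose, so they work as eligibility criteria, and it is natural to carry eligibility criteria over to controls. If that is the intention, this bias does not arise. That stands, but the text does not say so, and two analysts could build different control groups from it. The same timing also shows that these two filters can be applied to untreated patients without difficulty.

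A reader might infer that the exclusions themselves are the fault, or that they were justified only for sarcoma. The documents do not support either. Purpose, item 1a, says in general terms that patients with massive hemorrhage or underlying coagulopathy would not be suitable, and the Introduction explains the wish to begin with a moderate-risk sarcoma group. The exclusions are deliberate; the gap is in how controls are selected.

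It is also fair that the likely shift is usually smaller than sampling error and that the plan specifies no test against controls. This limits the weight of the point. It does not remove it, because a larger control group would not shrink the shift and a confidence interval would not show it.

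Finally, the calculation models only exclusion 5 and treats bloody fluid as if it were all drainage. Exclusions 4, 6 and 7 enter only through an assumed risk ratio. Other differences between historical and current patients could act in either direction.

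**Conclusion.** The point holds conditionally. The plan does not apply exclusions 4 to 7 to the controls. If controls are chosen by diagnosis and operation alone, the drainage comparison is likely shifted towards a finding of safety, mainly in sarcoma, provided that early and later drainage are not clearly negatively correlated. Transfusion and bleeding events shift the same way if the excluded patients have a higher risk.

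The size is unknown. The assumed grid gives a fall in the sarcoma mean from near 0% to about 30%, and more under wider spread. That range illustrates the mechanism and does not estimate the bias.

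A reader might infer that the trial's safety conclusion as a whole is compromised. The documents do not support that. The stopping rule under Safety Monitoring compares re-operations with fixed expected rates of 10% and 3%, not with the database controls. Statistical Considerations declines to base stopping on an amount of drainage. The control comparison is descriptive, and the data are called preliminary. This is a modest correction that should be made, at the lower end of that grade.

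**What to change.** State in Study Design that controls must meet the same inclusion and exclusion criteria as the trial patients, including 4 to 7, with the same measurements and time windows as far as recorded. Report how many trial patients and how many controls each criterion removes, and how many controls lack the data to be judged. Add a sensitivity analysis that includes the controls with missing records.

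Where timed drain data exist, also report drainage from a common time after the 8-hour window in both groups. This supplements the filter and cannot replace it: without filtered controls, sarcoma drainage after 8 hours is still 0% to 24% low in the assumed grid.

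The change needs a few sentences and some further extraction; no enrolment criterion or treatment rule is touched. The real cost is in the data. The items that Study Design lists for collection include drain output and transfusions but do not name 8-hour timing, blood loss, INR or platelets, although the list may not be complete. Some controls may be lost, and losing them could itself select patients, which is why the sensitivity analysis is needed.

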Consider risk versus benefit prior to neuraxial anesthesia. Risk is increased by concomitant agents which may alter hemostasis, as well as traumatic or repeated epidural or spinal puncture. Patient should be observed closely for bleeding if dalteparin is administered during or immediately following diagnostic lumbar puncture, epidural anesthesia, or spinal anesthesia.

Not to be used interchangeable (unit for unit) with heparin or any other low molecular weight heparins. Use with caution in patients with known hypersensitivity to

methylparaben or propylparaben. Use with caution in patients with history of heparin-induced thrombocytopenia. Monitor patient closely for signs or symptoms of bleeding. Certain patients are at increased risk of bleeding. Risk factors include bacterial endocarditis; congenital or acquired bleeding disorders; active ulcerative or angiodysplastic GI diseases; severe uncontrolled hypertension; hemorrhagic stroke; or use shortly after brain, spinal, or ophthalmology surgery; in patients treated concomitantly with platelet inhibitors; recent GI bleeding; thrombocytopenia or platelet defects; severe liver disease; hypertensive or diabetic retinopathy; or in patients undergoing invasive procedures. Use with caution in patients with severe renal failure (has not been studied). Safety and efficacy in pediatric patients have not been established. Rare cases of thrombocytopenia with thrombosis have occurred. Multidose vials contain benzyl alcohol and should not be used in pregnant women. Heparin can cause hyperkalemia by affecting aldosterone. Similar reactions could occur with LMWHs. Monitor for hyperkalemia.

Adverse Reactions

1% to 10%

Hematologic: Bleeding (3% to 5%), wound hematoma (0.1% to 3%)

Local: Pain at injection site (up to 12%), injection site hematoma (0.2% to 7%)

<1% (Limited to important or life-threatening):

Thrombocytopenia (including heparin-induced thrombocytopenia), allergic reaction (fever, pruritus, rash, injections site reaction, bullous eruption), anaphylactoid reaction, operative site bleeding, gastrointestinal bleeding, skin necrosis. Spinal or epidural hematomas can occur following neuraxial anesthesia or spinal puncture, resulting in paralysis. Risk is increased in patients with indwelling epidural catheters or concomitant use of other drugs affecting hemostasis.

Drug Interactions

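### Exclusion criteria 23 and 24 give the direct bilirubin and creatinine limits in gm/dL: the bilirubin limit does not fit its own mg/dl note, and the creatinine limit shows the same apparent slip

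*Combined protocol and SAP*

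**What the plan says.** The exclusion criteria under Materials and Methods (Patients) apply to both study groups. Three of them bear on this point.

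- **Criterion 23:** "Direct bilirubin >0.5 gm/dL (the laboratory does not perform direct bilirubin if total bilirubin is below 0.2 mg/dl"; the bracketed note goes on to give the reason, "since direct bilirubin cannot be greater than total bilirubin".
- **Criterion 24:** "Serum creatinine > 2.0 gm/dL".
- **Criterion 12:** "Severe liver or renal insufficiency", with no laboratory value attached.

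Criteria 21 and 22 set numeric limits for ALT and AST, and criterion 6 sets limits for INR. Neither the bilirubin nor the creatinine limit is restated elsewhere in another unit.

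The drug background section (Warnings/Precautions) explains why these organs matter. Its list of bleeding risk factors includes "severe liver disease; hypertensive or diabetic retinopathy; or in patients undergoing invasive procedures". On the kidney it says "Use with caution in patients with severe renal failure (has not been studied").

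**The concern.** Criterion 23 uses two mass units for bilirubin, a thousandfold apart, within one sentence. The limit is in grams and the note that helps to apply it is in milligrams. Criterion 24 also uses grams, for an analyte where that gives a very large number.

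These are working eligibility thresholds, not background text, in a study whose first hypothesis makes safe use conditional on strict guidelines. If the limits cannot operate as printed, the only numeric renal exclusion is lost, and so is one of several hepatic ones. If staff silently convert the unit, the exclusions applied are not those written, and eligibility cannot be audited against the protocol.

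**Working it through.** The plan states no derived figure on this point, so the check is a unit conversion and a test of whether the criterion 23 note works on each scale.

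**Inputs** (all from the exclusion criteria)

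- Direct bilirubin limit: 0.5 gm/dL (criterion 23).
- Total bilirubin level below which the direct assay is not run: 0.2 mg/dl (note to criterion 23).
- Creatinine limit: 2.0 gm/dL (criterion 24).
- Conversion: 1 gm = 1,000 mg.

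**Step 1. Limits as printed**

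- Direct bilirubin: 0.5 × 1,000 = 500 mg/dL.
- Creatinine: 2.0 × 1,000 = 2,000 mg/dL.

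**Step 2. Bilirubin limit against its own note**

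- As printed: 500 / 0.2 = 2,500.
- With both figures in mg/dL: 0.5 / 0.2 = 2.5.

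**Step 3. What the note does on each scale**

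The note's evident job is to show how a patient with no direct result can be judged against the limit. Direct bilirubin cannot exceed total, so a patient whose assay was skipped has direct ≤ total < 0.2 mg/dl.

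- *Limit of 0.5 on the mg scale:* 0.2 / 0.5 = 0.40 and 0.5 − 0.2 = 0.3. A skipped patient is below 40% of the limit, more than 0.3 mg/dl under it, so skipping cannot hide an exclusion. The direct assay still matters for patients with higher totals.
- *Limit of 500 mg/dL:* a skipped patient is again under the limit, but so is anyone whose total is below 500 mg/dL. A special explanation for totals below 0.2 mg/dl would serve no practical purpose.

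**Step 4. Creatinine**

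The documents give no creatinine figure in mg/dL, so this test cannot be repeated. The evidence is the implausibility of 2,000 mg/dL (general knowledge) and the same unit in the criterion directly above.

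**Step 5. What remains if both limits never apply**

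| Organ | Remaining exclusions |
|---|---|
| Liver | Criteria 12 (no number), 21 (ALT), 22 (AST); also 6 (INR), if INR is read as a liver marker, which the protocol does not say |
| Kidney | Criterion 12 only (no number) |

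**The case against.** The strongest reply is that nothing here is a strict contradiction. A testing floor of 0.2 mg/dl can coexist with any higher limit, 500 mg/dL included, and Step 3 confirms that the note's logic holds on both scales. This stands: the note shows that the gram reading is unnatural, not that it is impossible. Even so, a gm/mg slip is the most natural reading of criterion 23.

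Second, the creatinine half has no contradicting figure behind it, yet the main consequence, loss of the numeric renal limit, depends on that half. This also stands. It is why the creatinine limit is called an apparent slip and held with less confidence than the bilirubin limit.

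Third, the statement that the limits exclude nobody needs physiological ranges that the documents do not give. That is correct for both analytes, and it is treated below as an assumption.

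Fourth, the practical effect is close to nil. The note shows staff the milligram scale where they need it, and criterion 12 covers severe insufficiency, the level at which the background section urges caution. This limits the importance of the point, but it does not make the printed criteria correct.

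A PDF-reading fault cannot be wholly excluded. It is unlikely, because the same sentence prints mg/dl and the gram unit appears in two consecutive criteria.

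**Conclusion.** The concern holds, as a minor one. Criterion 23 is inconsistent in its units: its limit is 500 mg/dL as printed, 2,500 times the figure in its own note, and the note has a useful function only if both figures share a scale. Criterion 24, at 2,000 mg/dL as printed, very probably carries the same slip, on weaker evidence.

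Assuming, from general knowledge, that no patient reaches either value, both limits are inoperative as written. Hepatic function keeps other numeric criteria. Renal function is left to criterion 12, which has no numeric definition. The probable effect on who is enrolled is small, because staff would likely read mg/dL. No endpoint, sample size, power or stopping-rule figure is affected.

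**What to change.** Reconcile the units in criteria 23 and 24 with the note to criterion 23 and with the units in which the laboratory reports these tests. The clinical team should confirm the intended cut-offs; no limit is proposed here. If patients have already been screened, record which unit was used so that eligibility can be checked against the amended text.

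The cost is two unit corrections in an administrative amendment. No recalculation is needed.
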